### Intercurrent Events and Corresponding Strategies:

The following are the intercurrent events considered for this trial:

1. A Crohn's disease-related surgery (with the exception of minor procedures such as drainage of a superficial abscess or seton placement, etc.);
2. A prohibited change in CD medication;
3. Discontinuation of study intervention due to lack of efficacy or an AE of worsening Crohn's disease;
4. Discontinuation of study intervention due to COVID-19 related reasons (like missing the assessment visit due to COVID-19 quarantine, but excluding COVID-19 infection)
5. Discontinuation of study intervention due to reasons other than lack of efficacy or an AE of worsening Crohn's disease (including AE/SAE due to COVID-19 infection).

Intercurrent events (ICEs) in categories 1-3 will be handled by the composite strategy, and ICE category 4 will be handled by the hypothetical strategy (as if subjects would have not experienced this intercurrent event), and ICE category 5 will be handled by the treatment policy strategy. The composite strategy assesses the treatment effects not only based on the variable measurements, but also based on intercurrent events. This estimand acknowledges that having an intercurrent event in categories 1-3 is an unfavorable outcome, ie. baseline value will be used after ICEs. For subjects experiencing ICE category 4, CDAI data at all visits after an ICE will be set to missing with

assumption of missing at random. For ICE category 5, treatment policy strategy, the observed values after ICEs will be used, if available.

**Population-level summary:** The difference of change in the CDAI score at Week 12 between the Experimental treatment group and the placebo treatment group.

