### 5.3.3. Analysis Methods

#### 5.3.3.1. Main Estimator (Analysis) for the Primary Estimand

The primary analysis will be based on the full analysis set which will include all participants randomized and who receive at least 1 dose of the study intervention. Participants in the efficacy analyses will be summarized according to their assigned treatment arm regardless of whether or not they receive the assigned study intervention. The primary endpoint will be analyzed based on the primary estimand.

Data used in the primary analysis (i.e. the main estimator for the primary estimand) include all values for change from baseline in CDAI score collected up to and including Week 12 for all participants in the primary efficacy analysis set (ie, those who were randomly assigned to study intervention and received at least one dose of study intervention). Any CDAI score collected after experiencing intercurrent event categories 1-3 will be replaced by the baseline observation for CDAI. For subjects experiencing ICE category 4, CDAI data at all visits after an ICE will be set to missing with assumption of missing at random. For ICE category 5, treatment policy strategy, the observed values after ICEs will be used, if available.

The main estimator for the primary estimand is based on the Mixed Effects Model for Repeated Measures (MMRM), under the Missing at Random (MAR) assumption for the missing responses, the missing data will be accounted for through correlation of repeated measures in the model, to test the difference between the experimental group and the placebo group. The analysis will use change in CDAI scores at post-baseline time points through Week 12 as dependent variables. The explanatory variables of the MMRM model will include the fixed, categorical effects of treatment, time, and treatment-by-time interaction, as well as the continuous, fixed covariates of baseline and baseline-by-time interaction. If the intervention cohort includes both Bio-IR and Bio-NF participants, then the biologic therapy status will be included in the MMRM model as well. An unstructured variance-covariance structure will be used to model the within-participant errors. The treatment comparison at Week 12 in terms of the least square mean difference and confidence intervals for decision making will be estimated based on this model.

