The Week 12 SES-CD Total score will be calculated only if the participant has a Week 12 endoscopy and at least one segment is evaluable. For segments evaluated and scored at baseline but not at Week 12, associated baseline segment scores will be carried forward to calculate the Total SES-CD score at Week 12. Otherwise, the Week 12 Total SES-CD will be missing.

Participants who meet 1 or more treatment failure rules (as specified for the primary endpoint) before Week 12 will be considered not to be in clinical remission, clinical response or clinical-biomarker response, either based on CDAI or PRO-2. For endoscopic response, the same treatment failure rules will be applied as appropriate. Any missing values at week 12 will be considered as no responder/remitter.

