### Intercurrent Events and Corresponding Strategies:

The intercurrent events for all major secondary endpoints other than endoscopic response at Week 12 will be same as those used in the primary estimand, and are as follows:

1. A Crohn's disease-related surgery (with the exception of minor procedures such as drainage of a superficial abscess or seton placement, etc.);
2. A prohibited change in CD medication;
3. Discontinuation of study intervention due to lack of efficacy or an AE of worsening Crohn's disease;
4. Discontinuation of study intervention due to COVID-19 related reasons (like missing the assessment visit due to COVID-19 quarantine, but excluding COVID-19 infection)
5. Discontinuation of study intervention due to reasons other than lack of efficacy or an AE of worsening Crohn's disease (including AE/SAE due to COVID-19 infection).

ICEs will be handled by the same Estimands strategies as the primary Estimands strategies for the major secondary endpoints including clinical remission, clinical response, PRO-2 remission, endoscopic response (refer to Table 2 footnotes for ICE category 2), or endoscopic remission.

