#### **5.4.1.3. Analysis Methods for the Estimands for the Major Secondary Endpoints**

The major secondary endpoints of clinical remission (either based on CDAI, SES-CD, or PRO-2), clinical response, endoscopic response, and clinical-biomarker response at Week 12 will be compared between PTG-200 group and the placebo group.

A logistic regression model will be used in the responder analyses with the treatment arm and population status (Bio-IR or Bio-NF), if applicable, as fixed factors, at 2-sided significance level of 0.1. In this model, baseline measurements may be included as covariates as appropriate. The change from baseline in the SES-CD score at Week 12 will be evaluated using MMRM model in comparing treatment difference by LS Mean (SD), LS mean (90% CI). P-Value was based on comparison with placebo model. And other statistical analysis as appropriate.

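### For the five binary major secondary endpoints, the rule that a missing Week 12 value is non-response overrides the hypothetical strategy stated for COVID-19 discontinuations, so the stated estimand is not estimated

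*SAP*

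**What the plan says.** - SAP 5.3.2.1 (primary estimand): "ICE category 4 will be handled by the hypothetical strategy (as if subjects would have not experienced this intercurrent event". SAP 5.3.3.1 puts this into practice: "For subjects experiencing ICE category 4, CDAI data at all visits after an ICE will be set to missing with assumption of missing at random".
- SAP 5.4.1.2 (major secondary endpoints) lists the same five intercurrent events. Category 4 reads "Discontinuation of study intervention due to COVID-19 related reasons (like missing the assessment visit due to COVID-19 quarantine, but excluding COVID-19 infection". The section then states: "ICEs will be handled by the same Estimands strategies as the primary Estimands strategies for the major secondary endpoints". It goes on to name clinical remission, clinical response, PRO-2 remission, endoscopic response and endoscopic remission, which are all five binary endpoints. The only departure is a different medication list for ICE 2 in endoscopic response.
- SAP 5.4.1.1, on the same endpoints: "Any missing values at week 12 will be considered as no responder/remitter". SAP 5.4.2 repeats the sentence for the supportive endpoints.
- SAP 5.4.1.3 gives the estimator: "A logistic regression model will be used in the responder analyses with the treatment arm and population status (Bio-IR or Bio-NF", with baseline measurements as optional covariates. It describes no imputation or other MAR step.

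**The concern.** The two instructions lead to opposite results for the same participant. The hypothetical strategy asks what would have happened had the COVID-19 disruption not occurred. The missing-value rule answers that the participant would not have responded. The rule even reaches people who were observed. The Schedule of Activities asks participants who stop study intervention to keep attending visits. An ICE 4 participant seen in remission at Week 12 would have that value set to missing and would then be counted as a non-remitter.

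Two things are at stake. First, the reported estimand would not be the one analysed. Clinical response and remission derive from the same CDAI as the primary endpoint, so one ICE 4 participant would be MAR in the primary test and a non-responder in the next tests of the same hierarchy. Second, the response difference is distorted by events that the plan treats as unrelated to drug effect.

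**Working it through.** **The text, step by step, for one ICE 4 participant**
1. SAP 5.4.1.2 sends us to the primary estimand's strategy, which is hypothetical for ICE 4.
2. SAP 5.3.2.1 and 5.3.3.1 set data after the event to missing, under MAR.
3. SAP 5.4.1.1 turns the missing Week 12 value into non-response.
4. SAP 5.4.1.3 enters that non-response into the logistic model.

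The outcome is the handling that SAP 5.3.3.3 calls a composite strategy. Estimand 2 there differs from Estimand 1 only in treating ICE 4 and 5 like ICE 1–3, so the SAP itself counts this as a different estimand. The only precedence rule, in SAP 5.3.1, concerns treatment failure rules and does not settle the matter.

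**The plan's own figure.** No rate or power is stated for the binary endpoints. The nearest figure is the primary power of about 90% (SAP 3: difference 60, SD 93; 54 v 36; two-sided 0.1). The standard error is 93 × √(1/54 + 1/36) = 20.0, and 60/20.0 − 1.645 = 1.35, giving power 0.91. It reproduces.

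**Derived response rates.** The inputs are the Week 0 and Week 12 CDAI means, variances and covariances in SAP Attachment 2 (protocol Appendix 6), with an equal mix of Bio-IR and Bio-NF. Clinical response is a fall of at least 100 points or a Week 12 CDAI below 150. I took rates from bivariate normal draws, 2 million per arm and population.
- Active 53.999%, placebo 30.275%, difference 23.7 points. Direct bivariate normal calculation gives 54.02% and 30.31%; the differences below then move by no more than 0.1 point.
- Clinical remission can be checked by hand. The Week 12 SD is √11025 = 105. Active: Φ((150−238)/105) = 0.201 and Φ((150−176)/105) = 0.402, mean 30.1%. Placebo: Φ((150−298)/105) = 0.079 and Φ((150−236)/105) = 0.206, mean 14.3%.

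**Effect of the rule.** If a share d of an arm has ICE 4 and would otherwise have responded at the arm's rate p, the non-response rule gives p × (1 − d). The shares d are assumptions.

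| ICE 4 share, active / placebo | Clinical response, active v placebo | Difference (target 23.7) |
|---|---|---|
| 5% / 5% | 51.3% v 28.8% | 22.5 |
| 10% / 10% | 48.6% v 27.2% | 21.4 |
| 15% / 15% | 45.9% v 25.7% | 20.2 |
| 10% / 0% | 48.6% v 30.3% | 18.3 |
| 0% / 10% | 54.0% v 27.2% | 26.8 |

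For clinical remission the target difference is 15.9 points. It becomes 15.1, 14.3 and 13.5 at equal shares of 5%, 10% and 15%, and 12.9 or 17.3 at 10% / 0% or 0% / 10%.

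**Scale.** The standard error of the response difference is √(0.540 × 0.460/54 + 0.303 × 0.697/36) = 10.2 points. Equal shares of 5% and 10% therefore cost about 0.12 and 0.23 standard errors (1.2/10.2 and 2.4/10.2). Power for clinical response is 0.73 with no ICE 4. At equal shares of 5% to 15% it falls to 0.69–0.62 under the rule, against 0.71–0.66 for a MAR analysis of the remaining participants.

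**The case against.** The strongest defence is that intercurrent-event strategy and missing-data handling are separate layers, and that non-response for missing values is conventional and cautious. The first part does not save the text, because the SAP makes MAR part of its ICE 4 strategy, and scoring every missing value as failure is not MAR. Nor is the rule reliably cautious, since an excess of ICE 4 on placebo inflates the difference.

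Other objections do stand, and they limit the point:
- The subgroup is probably small. Study intervention is self-administered daily, and protocol Appendix 7 allows remote, in-home or delayed visits. Under blinding, COVID-19 logistics should not differ systematically by arm, so imbalance would mostly be chance.
- Much of the power loss comes from losing data at all. The rule itself costs about 2 to 4 percentage points at equal shares of 5% to 15%.
- The success and futility criteria in Attachment 1 use only change in CDAI and change in SES-CD. The binary endpoints are tested only after the primary succeeds.

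A reader might infer stronger claims that the documents do not support:
- *Everyone who misses Week 12 for quarantine becomes a treatment failure.* Treatment failure is a defined list in SAP 5.3.1, and these participants are non-responders by a separate sentence. ICE 4 is discontinuation of study intervention. Someone who stays on drug and only misses the visit has ordinary missing data, although the example in the ICE 4 wording blurs this.
- *Logistic regression cannot be valid under MAR.* It can, if ICE 4 participants are left out and their missingness depends only on arm, population and included baseline covariates.
- *The non-response rule is wrong throughout.* It agrees with the composite strategy for ICE 1–3. For ICE 5, where observed values are used if available, it is a missing-data choice and not a contradiction.

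**Conclusion.** The SAP is wrong as written on this point, and the contradiction needs no calculation to establish. For the five binary major secondary endpoints, ICE 4 is declared hypothetical and handled as composite. The MAR sentences are written for CDAI data and reach PRO-2 and the endoscopic endpoints through the cross-reference in SAP 5.4.1.2.

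The size is conditional. It depends on an ICE 4 share that the documents do not give and on response rates derived from Attachment 2, which states CDAI means and covariances but no response rates. When the arms are balanced the effect is modest and towards zero; when they are not, it can go in either direction. With no ICE 4 cases the two rules coincide. This should be corrected before unblinding, but it does not bear on the stated success and futility criteria.

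**What to change.** - In SAP 5.4.1.1 and 5.4.2, exempt ICE 4 from the missing-equals-non-response rule.
- In SAP 5.4.1.3, name a MAR method for those participants. One option is multiple imputation of the underlying CDAI and of the abdominal pain and stool frequency scores, followed by dichotomising. The other is a logistic model that omits them and includes baseline covariates.
- Keep non-response for all missing values as a sensitivity analysis.
- For endoscopic response and remission, either do the same or state openly that ICE 4 is composite. There is one post-baseline endoscopy, and Attachment 2 assumes a correlation of only 0.15 between SES-CD change and Week 12 CDAI, so imputation would be weakly informed.
- In the same revision, reconcile SAP 5.3.1, which assigns no change to a missing Week 12 CDAI, with SAP 5.3.3.1, which relies on the repeated-measures model under MAR.

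The cost is SAP wording and a small extension of the imputation code. The multiple imputation now planned under Estimand 4 covers change in CDAI only, so the abdominal pain and stool frequency scores, and SES-CD if chosen, would have to be added. Protocol Appendix 7 already requires COVID-19-related discontinuations to be labelled in the case report form, so ICE 4 participants can be identified.

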#### 5.4.1.2. Estimands

The following describes the attributes of the estimands for the major secondary endpoints:

**Treatment by Week 12:** Same as Estimand 1, ie:

**Treatment:** CCI [REDACTED] for a 12 weeks period

- Experimental: JNJ-67864238 (PTG-200), CCI [REDACTED]
- Control: Matching Placebo tablets CCI [REDACTED]

**Population:** Participants with moderately to severely active Crohn's disease,

#### Variables and Population-level Summary (for Estimands 5-10)

**Table 2: Variables and Population-level Summary for the estimand for each Major Secondary Endpoint**

Estimand	Variable (Endpoint)	Population-level summary
5	Change in the SES-CD from baseline (both main approach and alternative approach analyses will be performed )	Change from baseline in the SES-CD score at Week 12 or early withdrawal visit between experimental group and placebo.

6	Clinical response as measured by CDAI ( $\geq 100$ -point reduction from baseline in CDAI or CDAI $< 150$ )	Difference in percentage of subjects who achieved clinical response at Week 12 between experimental group and placebo.
7	Clinical remission rate as measured by CDAI (CDAI $< 150$ )	Difference in percentage of subjects who achieved clinical remission at Week 12 between experimental group and placebo.
8	PRO-2 remission defined as abdominal pain (AP) mean daily score (AP component of the CDAI) at or below 1 AND stool frequency (SF) mean daily score at or below 3, ie, AP $\leq 1$ and SF $\leq 3$	Difference in percentage of subjects who achieved PRO-2 remission at Week 12 between experimental group and placebo.
9*	Endoscopic response (defined as at least a 50% improvement from baseline in the SES-CD) (both main approach and alternative approach analyses will be performed )	Difference in percentage of subjects who achieved endoscopic response at Week 12 between experimental group and placebo.
10	Endoscopic remission (defined as an SES-CD score $\leq 2$ ) (both main approach and alternative approach analyses will be performed )	Difference in percentage of subjects who achieved endoscopic remission at Week 12 between experimental group and placebo.

\* For Endoscopic response, please refer to below prohibited medications for ICE category 2

- Immunomodulatory agents other than AZA, 6-MP, or MTX (including, but not limited to, 6-TG, cyclosporine, mycophenolate mofetil, tacrolimus, and sirolimus).
- Immunomodulatory biologic agents (including, but not limited to, TNF antagonists, natalizumab, ustekinumab, rituximab, vedolizumab). Ustekinumab is permitted in this study only in participants randomly assigned to ustekinumab and only as stipulated in this protocol.
- Experimental Crohn's disease medications (including, but not limited to, upadacitinib, filgotinib, ozanimod, etrolizumab, brazikumab, mirakizumab [formerly LY-3074828], risankizumab, GS-5745)
- Thalidomide or related agents.

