4. STUDY DESIGN

4.1. Overall Design

This ISA is designed to assess the effects of a predominantly gastrointestinal-restricted anti-IL-23R compound for moderately to severely active Crohn's disease. This 12-week Phase 2a study is focused on proof-of-concept and will assess the safety and efficacy of an orally administered high dose of JNJ-67864238 compared with placebo in participants with Crohn's disease. Since the inhibition of the IL-23 pathway has been validated as a mechanism for treating Crohn's disease, a high dose was chosen to assess the efficacy of a locally acting anti-IL-23 inhibitor.

The target population for this intervention cohort is defined in Section 4.1.2 of the Master protocol PLATFORMPACRD2001 (ie, men or women 18 to 75 years of age with moderately to severely active Crohn's disease of at least 3 months' duration, defined as a Crohn's Disease Activity Index (CDAI) score ≥ 220 but ≤ 450 at Week 0, with a Simplified Endoscopic Score for Crohn's disease (SES-CD) score ≥ 3 by central endoscopy read OR an elevated C-reactive protein (CRP; >0.3 mg/dL or 3.0 mg/L) or elevated fecal calprotectin (>250 μ g/mg). In this intervention cohort, however, participants with a screening SES-CD score <3 who have an elevated CRP or elevated fecal calprotectin will be limited to 20% of the participant population.

Participants may be biologic intolerant or refractory (Bio-IR) or biologic nonfailures (Bio-NF) populations as defined in Section 4.1.2 of the Master protocol PLATFORMPACRD2001.

A target of 90 Bio-IR and Bio-NF participants will be randomized to receive JNJ-67864238 CCI [REDACTED] or placebo in a 3:2 ratio using permuted block randomization, stratified by baseline CDAI score (≤ 300 , >300) and biological refractory status (Bio-IR, Bio-NF). The treatment arms for this study will be as follows:

- JNJ-67864238 CCI [REDACTED] (N=54)
- Placebo (N=36)

Of note, the sample size has been chosen to assess a level of efficacy consistent with that observed with systemically available biological therapies for Crohn's disease (Section 2.1 of this ISA).

There is 1 database lock (DBL) planned at the end of this intervention cohort. In addition, there will be a planned Interim Analysis (IA) to enable early termination of the intervention cohort if JNJ-67864238 (CCI [REDACTED]) is futile. Additional ad hoc IA(s) may be conducted if deemed necessary. No DBLs are planned for any of the IA(s).

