5.1. Inclusion Criteria

Each potential participant must satisfy all of the following Master PLATFORMPACRD2001 protocol and these ISA-specific criteria to be enrolled in the JNJ-67864238 intervention cohort.

Master PLATFORMPACRD2001 protocol inclusion criteria are listed below.

1. Male or female
2. 18 to 75 years of age, inclusive

Disease Characteristics

3. Have Crohn's disease or fistulizing Crohn's disease of at least 3 months' duration, with colitis, ileitis, or ileocolitis confirmed at any time in the past by radiography, histology, and/or endoscopy
4. Have active Crohn's disease, defined as a baseline CDAI score of ≥ 220 and ≤ 450
5. Have evidence of active ileocolonic Crohn's disease as assessed by:
 - a. An SES-CD score ≥ 3 at screening by central endoscopy reading
OR
 - b. An elevated screening CRP (>0.3 mg/dL or 3.0 mg/L) or an elevated screening fecal calprotectin (>250 μ g/mg)
6. A participant with a family history of colorectal cancer, personal history of increased risk of colorectal cancer, age >50 years, or other known risk factor must be up-to-date on colorectal cancer surveillance (may be performed during screening). Adenomatous polyps must be removed before the first administration of the study intervention.

7. A participant who has had extensive colitis for ≥ 8 years, or disease limited to the left side of the colon for ≥ 12 years, must either have had a colonoscopy to assess for the presence of dysplasia within 1 year before the first administration of the study intervention or a colonoscopy to assess for the presence of malignancy at the screening visit, with no evidence of malignancy

Concomitant or Previous Medical Therapies Received

8. Meet the following requirements for prior or current medications for Crohn's disease:
 - a. Has previously demonstrated inadequate response to, loss of response to, or intolerance to an approved biologic therapy (unless otherwise specified in the JNJ-67864238 intervention cohort specific criteria below, ie, anti-TNF α agents [eg, infliximab, adalimumab, certolizumab pegol], anti-IL-12/23 agents [eg, ustekinumab], or anti-integrin agents [eg, vedolizumab]), ie, the Bio-IR population (Appendix 2 of the Master protocol PLATFORMPACRD2001 [Definition of Inadequate Initial Response, Loss of Response, or Intolerance to TNF Antagonist Therapies (Infliximab, Adalimumab, or Certolizumab Pegol), Vedolizumab, or Ustekinumab] and Section 5.2 of this ISA)

OR

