### **5.3.2. Estimand**

#### **5.3.2.1. Primary Estimand (Estimand 1)**

The primary estimand uses a Composite Strategy that considers meeting the treatment failure (TF) criteria as an unfavorable outcome. This strategy aims to achieve an objective treatment effect.

The primary estimand, the main clinical quantity of interest to be estimated in the study, is defined by the following components:

**Treatment:** Oral tablets CCI [REDACTED] for a 12 week period

- Experimental: JNJ-67864238 (PTG-200), CCI [REDACTED]
- Control: Matching Placebo tablets CCI [REDACTED]

**Population:** Participants with moderately to severely active Crohn's disease, The target population consists of men or women 18 to 75 years of age with moderately to severely active Crohn's disease of at least 3 months' duration, defined as a CDAI score  $\geq 220$  but  $\leq 450$  at Week 0, with an SES-CD score  $\geq 3$  by central endoscopy read. Participants with a screening SES-CD score  $< 3$  can be randomized and received at least one study dose if they have an elevated CRP ( $> 0.3$  mg/dL or 3.0 mg/L) or elevated fecal calprotectin ( $> 250$   $\mu\text{g/g}$ ). Participants must have colitis, ileitis, or ileocolitis previously confirmed at any time in the past by radiography, histology, and/or endoscopy. Participants must be biologic intolerant or refractory (Bio-IR) or biologic nonfailures (Bio-NF) and must be on a stable dose of at least 1 protocol-permitted therapy for the treatment of Crohn's disease prior to baseline and not receiving any protocol-prohibited therapies. For more details and for a complete list of inclusion/exclusion criteria, please refer to the protocol.

**Variable (Endpoint):** Change from baseline in the CDAI score at Week 12. Participants who have intercurrent events in categories 1-3 (defined below) prior to the Week 12 visit will have their baseline CDAI score assigned, regardless of the observed data.

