## 5.4. Secondary Endpoint(s) Analysis

### 5.4.1. Key Confirmatory Secondary Endpoint

#### 5.4.1.1. Definition of Endpoint(s)

The major secondary endpoints include the following at Week 12:

- Change in the SES-CD from baseline
- Clinical response as measured by CDAI ( $\geq 100$ -point reduction from baseline in CDAI or CDAI  $< 150$ )
- Clinical remission rate as measured by CDAI (CDAI  $< 150$ )
- PRO-2 remission defined as abdominal pain (AP) mean daily score (AP component of the CDAI) at or below 1 AND stool frequency (SF) mean daily score at or below 3, ie, AP  $\leq 1$  and SF  $\leq 3$
- Endoscopic response (defined as at least a 50% improvement from baseline in the SES-CD)
- Endoscopic remission (defined as an SES-CD score  $\leq 2$ )

The (SES-CD) is a scoring system developed to provide a more granular evaluation of endoscopic disease severity in patients with Crohn's disease. It is constructed based on the evaluation of 4 endoscopic components across 5 predefined ileocolonic segments. The 4 endoscopic components within each segment are: the presence/ size of ulcers, the proportion of mucosal surface covered by ulcers, the proportion of mucosal surface affected by any other lesions, and the presence/ type of narrowing (also commonly referred to as strictures/ stenosis clinically). Each endoscopic component is scored from 0 to 3 for each segment, and a total score is calculated as a sum of all the component scores across all the segments, as outlined in [Attachment 4](#). The total SES-CD score ranges from 0 to 56.

Calculation of the SES-CD score:

Main approach (SES-CD calculated based on all segments available):

The total SES-CD score at a visit will be calculated based on all segments scored at the visit. If the total SES-CD score cannot be calculated (i.e., no segment is scored) at a visit, the total SES-CD score will be considered missing.

Alternative approach (baseline segments matched approach):

To calculate the SES-CD score at a visit, the sum of the segments that were present at baseline will be used. For segments that were present at baseline but missing post-baseline, the baseline score for the missing segment(s) will be carried forward. In the event that a segment is missing at baseline but non-missing at post-baseline, the non-missing post-baseline score is not used in the calculation of SES-CD.

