#### **5.4.2. Supportive Endpoint(s)**

Other endpoints to be evaluated across all post-baseline visits as appropriate:

- Change in AP from baseline based on a 0 to 10 numerical rating scale (NRS)
- Change in number of daily loose or watery stools
- Changes from baseline in the CDAI, PRO-2 (the sum of AP and SF subscores of the CDAI score), PRO-3 (the sum of AP, stool frequency, and general well-being subscores of the CDAI score), C-reactive protein (CRP), and fecal calprotectin
- Clinical remission (CDAI <150), PRO-2 remission (AP  $\leq$ 1 and SF  $\leq$ 3), and clinical response based on CDAI
- Endoscopic improvement based on a reduction from baseline in the SES-CD score ( $\geq$ 3 points, 25%, 50%), (both main approach and alternative approach analyses will be performed)
- Endoscopic healing (defined as the absence of mucosal ulcerations), (both main approach and alternative approach analyses will be performed)
- Patient's Global Assessment of Crohn's Disease Activity
- Change from baseline in multivariate score of biomarkers measured in mucosal biopsy samples, whole blood, serum, and/or stool
- Change in PROs as measured by the PROMIS-29 score

ICEs will be handled by the same Estimands strategies as the primary Estimands strategies for the supportive secondary endpoints. Participants who do not return for evaluation or have missing AP or SF scores at Week 12 will be considered not to be in PRO-2 remission (ie, clinical remission measured by AP and SF). Participants who do not return for evaluations or have missing CRP or fecal calprotectin values at Week 12 will be considered not to be in clinical-biomarker response unless the non-missing values at Week 12 already confirm a clinical-biomarker response. Any missing values at week 12 will be considered as no responder/remitter.

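### Endoscopic response and the SES-CD improvement endpoints set no minimum baseline score, although up to 20% of participants may enter with SES-CD 0-2

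*SAP*

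**What the plan says.** **Endpoints.** SAP Table 2, Estimand 9, is "Endoscopic response (defined as at least a 50% improvement from baseline in the SES-CD", analysed under both SES-CD scoring approaches. SAP 5.4.2 adds "Endoscopic improvement based on a reduction from baseline in the SES-CD score", at thresholds of 3 points, 25% and 50%. Neither place sets a minimum baseline score. SAP 5.4.1.1 gives the scale: "The total SES-CD score ranges from 0 to 56".

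**Entry.** Protocol 5.1, criterion 5, accepts an SES-CD of at least 3 or, as an alternative, an elevated CRP "or an elevated screening fecal calprotectin". SAP 5.3.2.1 repeats this: participants with a screening score below 3 "can be randomized and received at least one study dose if they have an elevated CRP" or calprotectin. Protocol 4.1 adds a ceiling: those with a score below 3 "who have an elevated CRP or elevated fecal calprotectin will be limited to 20% of the participant population". No lower limit is given, so a score of 0 is eligible. SAP Table 5 has a baseline category for scores 0 to 2, labelled as remission.

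**Analysis set and missing data.** The full analysis set (SAP 4) is everyone randomised and dosed, with no SES-CD condition. The responder rule in SAP 5.4.1.1 is "Any missing values at week 12 will be considered as no responder/remitter". It addresses a missing Week 12 value. The two scoring approaches in the same section address unscored segments. None of these covers a low baseline score.

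**The concern.** A percentage fall needs a baseline with room to fall. For participants entering at 0, 1 or 2, the three thresholds behave differently from one another and from the way they behave at higher scores. One cannot be met, and the percentage thresholds are undefined at 0 and are met by a single point at 1 or 2.

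Estimand 9 is tested under the gatekeeping procedure at an overall two-sided alpha of 0.1. Its outcome should not turn on a programming choice for anyone, and a one-point change in someone already in the SAP's remission category is weak evidence of endoscopic response. If such events are about equally common in both arms, they raise both response rates and dilute the difference. A score below 3 is not a stratification factor, so the group may also be unevenly split between arms, and a coding choice could then shift the estimated difference.

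**Working it through.** **Plan's own figure.** The documents give no power for endoscopic response. The only related figure is about 90% for CDAI (SAP 3: difference 60, SD 93; 54 v 36; two-sided alpha 0.1). It reproduces: SE = 93 × √(1/54 + 1/36) = 20.0, and Φ(60/20.0 − 1.645) = 0.91. This point does not depend on it.

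**Step 1: size of the group.** 20% × 90 = 18 at most, or about 11 active and 7 placebo if balanced (0.2 × 54 = 10.8; 0.2 × 36 = 7.2). If 18 enrol and are allocated without regard to SES-CD, a hypergeometric calculation gives a 29% chance that the arms differ by 10 percentage points or more in their share.

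**Step 2: what each threshold requires.** This uses only the definitions and the floor of 0.

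| Baseline SES-CD | Points needed for 50% | Points needed for 25% | 3-point fall possible? |
|---|---|---|---|
| 0 | undefined | undefined | no |
| 1 | 1 | 1 | no |
| 2 | 1 | 1 | no |
| 3-4 | 2 | 1 | yes |
| 5-6 | 3 | 2 | yes |

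At baseline 0 with no change, (baseline − Week 12)/baseline is 0/0. A program using that formula returns missing, probably read as non-response. A program testing whether Week 12 is at most half of baseline finds 0 ≤ 0 and returns a response.

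**Step 3: power for Estimand 9.** Assumptions, none of them from the documents: response 30% v 10% at baseline 3 or more, a 20% share at 0-2, and no drug effect in that group, which responds at rate q in both arms. The full-set rates are then 0.8 × 0.30 + 0.2q and 0.8 × 0.10 + 0.2q. Power is by exact enumeration of two binomials with the pooled z-test at 1.645.

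| Analysis | Rates | n | Power |
|---|---|---|---|
| Restricted to baseline 3 or more | 30% v 10% | 43 v 29 | 66% |
| Full set, q = 0 | 24% v 8% | 54 v 36 | 66% |
| Full set, q = 10% | 26% v 10% | 54 v 36 | 62% |
| Full set, q = 20% | 28% v 12% | 54 v 36 | 59% |
| Full set, q = 40% | 32% v 16% | 54 v 36 | 54% |

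**Step 4: relaxing the no-effect assumption.** If the drug works equally well at 0-2 (30% v 10% there too), the full set has 77% power and the restricted set 66%. At 30% v 20% in the low group, the two are about equal at 66%.

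**The case against.** **The ordinary reading settles baseline 0.** Someone who stays at 0 has not improved, so most programmers would return non-response, and if the whole 0-2 group never responds no power is lost. This is fair as a prediction of what would be done. It is not a written rule: at baseline 0 the Week 12 score is observed, so the missing-data sentence does not clearly apply. It also leaves baseline 1 and 2 untouched, where the stated definition counts a one-point fall.

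**The group need not be near-automatic responders.** A reader might infer that they are, and put the power loss at 12 to 19 points. The documents do not support that. At 1 or 2 a real fall on endoscopy is still needed, and treatment failures and missing values count as non-response. Losses of that size need 40% to 100% response in both arms and the full 20% share, which is a ceiling rather than an expected figure. At 10% to 20% response the loss is 4 to 7 points.

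**Restriction is not free.** This stands. It costs almost nothing only if the drug has no effect at 0-2. A fall from 2 to 0 is genuine improvement, and the SAP's target population includes these participants. Keeping the full set and declaring 0-2 non-responders is a legitimate alternative.

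**The stakes are limited.** This also stands. The success and futility rules use change in CDAI and change in SES-CD, not Estimand 9. Estimand 9 is tested only if the primary endpoint succeeds, and the endpoints in SAP 5.4.2 are supportive.

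**The Master protocol might hold a rule.** Protocol 9.4.3 refers to it for secondary endpoints, and it was not available for this review. If a rule is there, the SAP should cite it.

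**Conclusion.** The gap is real and follows from the definitions alone. Entry at SES-CD 0-2 is deliberately allowed, the 25%, 50% and 3-point endpoints have no baseline floor, and no rule in the two documents covers this group. At most 18 of 90 participants are affected.

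The effect on power is uncertain and probably modest. Under the stated assumptions it runs from nothing, if the group never responds, through 4 to 7 points at 10% to 20% response, to 12 points at 40%. It reverses if the drug works as well at 0-2 as elsewhere. All response rates are assumptions, and the share is taken at its ceiling. A reader might go further and conclude that the trial's main result is compromised. The documents do not support that, because neither the primary endpoint nor the decision rules use these endpoints. The correction belongs in the SAP before unblinding.

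**What to change.** In SAP Table 2 (Estimand 9) and SAP 5.4.2, state that endoscopic response and the 3-point, 25% and 50% SES-CD improvements are analysed in full-analysis-set participants with baseline SES-CD of at least 3. Report as a sensitivity analysis the full set with baseline 0-2 counted as non-responders. The reverse order, with the full set as the main analysis and the restricted set as the sensitivity analysis, is equally acceptable and has about the same power (66% either way under the no-effect assumption). What matters is that one is named in advance.

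Leave change in SES-CD (Estimand 5) in the full set, since it is defined at any baseline. When making the edit, also consider Estimand 10: anyone entering at 0-2 already meets the remission threshold of 2 or below.

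The cost is SAP wording only. The baseline score is already collected, and selecting on it keeps the randomised comparison. The restricted analysis has up to 20% fewer participants (about 72 instead of 90), no longer covers the whole target population, and would lose power if the drug also works at 0-2.
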